	Possible worsened vision	xx (xx%)	xx (xx%)	xx (xx%)
	Definite worsened vision	xx (xx%)	xx (xx%)	xx (xx%)
	Left n	xx	xx	xx
	No change/improved vision	xx (xx%)	xx (xx%)	xx (xx%)
	Possible worsened vision	xx (xx%)	xx (xx%)	xx (xx%)
	Definite worsened vision	xx (xx%)	xx (xx%)	xx (xx%)
Maximum (worst) change from baseline	Right n	xx	xx	xx
	No change/improved vision	xx (xx%)	xx (xx%)	xx (xx%)
	Possible worsened vision	xx (xx%)	xx (xx%)	xx (xx%)
	Definite worsened vision	xx (xx%)	xx (xx%)	xx (xx%)

CONFIDENTIAL

BMA117159

Left	N	xx	xx	xx
	No change/improved vision	xx (xx%)	xx (xx%)	xx (xx%)
	Possible worsened vision	xx (xx%)	xx (xx%)	xx (xx%)
	Definite worsened vision	xx (xx%)	xx (xx%)	xx (xx%)

Note: High scores are associated with worse vision, and low scores with better vision. No change/improved vision is defined as a change from baseline <0.12 ; a possible worsened vision is defined as a change from baseline ≥ 0.12 to <0.3 ; a definite worsened vision is defined as a change from baseline ≥ 0.3 logMAR score. For "End of study Treatment", summarize for subjects with ocular exam results at the end of study treatment; ocular assessment For "Change from baseline to end of study treatment", summarize for subjects with ocular exam results at baseline and the end of study treatment. For "Maximum (worst) change from baseline", summarize for subjects with ocular exam results at baseline and at least one post-baseline visit.

Subjects with "worse than 20/400" results will not be included in the summary.

PPD

Example: SAFE_T3
Protocol: BMA117159
Population: Part 1

Page 1 of 1
(Data as of: 30MAY2001)

Table x.xxxx
Summary of Symptom Impact and HRQoL Item Scores Part 1)

Item Score=Bone Pain Worst
Treatment: 0.03 mg/kg (N=200)

Planned Time		n	Mean	SD	Median	Min.	Max.
Baseline	Score	xx	xx.x	xx.xx	xx	xx	xx
Cycle 1 Day 1 to Day 8 Average	Score	xx	xx.x	xx.xx	xx	xx	xx
	Change from Baseline	xx	xx.x	xx.xx	xx	xx	xx
Cycle 1 Day 15	Score	xx	xx.x	xx.xx	xx	xx	xx
	Change from baseline	xx	xx.x	xx.xx	xx	xx	xx

Note: This mock up will be used for both summary of item scores and change from baseline. For summary of change from baseline, include baseline scores. Include Bone Pain Worst, Bone Pain Average, Fatigue worst in one summary table. This note dose not need to be included in the final output. Will add the notes to programming notes

PPD

Example: SAFE_T4
 Protocol: BMA117159
 Population: Part 1

Page 1 of 1
 (Data as of: 30MAY2001)

Table X.XXXX

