2.2. Study Objective(s) and Endpoint(s)

Objectives	Endpoints
Primary Objectives	Primary Endpoints

 To determine safety, tolerability, maximum tolerated dose (MTD), and recommended phase (RP2) dose and schedule of GSK2857916 administered 	
 Adverse events (AE) and changes in clinical signs and laboratory parameters
Secondary Objectives	Secondary Endpoints

 To evaluate the pharmacokinetic (PK) profile of GSK2857916 and the breakdown product cys-mcMMAF after intravenous (IV) single and repeat dose administration in subjects with relapsed/refractory MM and BCMA expressing lymphomas 	
 GSK2857916 and cys-mcMMAF PK parameters following IV single and repeat dose administration during dose escalation as data permit (e.g., AUCs C_{max}, t_{max}, CL, V_{ss}, t_{1/2} [single dose], C_{max} and C_{trough} [repeat dose]). GSK2857916 population PK parameters in expansion cohorts at the RP2 dose (e.g. clearance (CL), volume of distribution (V_d)), and relevant covariates which may influence exposure (e.g. age, weight, or disease-related covariates e.g. BCMA expression)

 To assess anti-drug antibody (ADA) formation after IV single and repeat dose administration of GSK2857916 	
 ADA incidence and titers after single and repeat IV dosing of GSK2857916

 To explore the initial anti-tumor activity of GSK2857916 in subjects with relapsed/refractory MM and BCMA expressing lymphomas 	
 Clinical activity measured as Overall Response Rate (ORR) which is defined as follows: 
 For MM: the percentage of subjects achieving confirmed partial response or better (≥PR) In addition, the percentage of subjects with minimal response (MR) will be assessed for clinical benefit rate (CBR) (Appendix 1 of protocol) For Lymphomas: the percentage of subjects achieving PR or better (≥PR) (Appendix 2 of protocol)
Exploratory Objectives	Exploratory Endpoints

 To evaluate PD markers in MM after treatment with GSK2857916 	
 sBCMA levels, BCMA receptor occupancy and cell death markers in subjects with MM.

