3.1.1.1. Description of the New Continual Reassessment Method

The N-CRM is a type of Bayesian adaptive dose-escalation scheme that estimates the parameters of a statistical model relating dose and toxicity, and is expected to locate the MTD efficiently while minimizing the number of subjects exposed to pharmacologically inactive or unsafe dose levels. The method is fully adaptive and makes use of all the toxicity information available at the time of each dose assignment. N-CRM estimates may be provided at dose escalation meetings as supportive material to the primary 3+3 dose escalation design.

The N-CRM estimates, for each potential dose, the (Bayesian) posterior probabilities that the DLT rate lies in each of four predefined toxicity ranges:

- A dose falls in the **Under-dosing** range if the rate of a DLT at the dose is in the interval [0%, 16%).
- A dose falls in the **Target** toxicity range if the rate of a DLT at the dose is in the interval [16%, 33%).
- A dose falls in the **Excessive** toxicity range if the rate of a DLT at the dose is in the interval [33%, 60%).

- A dose falls in the **Unacceptable** toxicity range if the rate of a DLT at the dose is in the interval [60%, 100%].

Additionally, the following over-dose constraints for the recommended dose will be maintained:

- The posterior probability of the DLT rate lying in the Excessive Toxicity or Unacceptable Toxicity range is 0.25 or less.
- The recommended dose is no more than 2 times that of the previous dose.
- Note that a de-escalation recommendation is possible using this method. At the time of each dose-escalation decision, the dose with the highest posterior probability of lying in the Target Toxicity range (subject to the given constraints) will be the model-recommended dose for the next cohort.

The N-CRM procedure for Schedule 1 will utilize a single subject/cohort run-in phase.

The single subject (small cohort) run-in will be halted when the first \geq Grade 2 toxicity for which relationship to the investigational agent cannot be ruled out occurs in one subject in Cycle 1 (21 days). At this point, the cohort will be expanded to 3 or more subjects at the same dose level and the escalation will continue to follow the N-CRM procedure as outlined in [Table 2](#)

Table 2 Single Subject (Small Cohort) Run-In Procedure for GSK2857916 given on Schedule 1 (once every 21 days)

Dose Level	Number of subjects with \geq G2 toxicity	Dose Escalation/Action

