Absolute change from baseline in LVEF will be summarized in the worst case post-baseline only. Only the post-baseline assessments that used the same method (ECHO or MUGA) as the baseline assessments will be used to derive the change from baseline. The change from baseline will be categorized as follows:

- No change or any increase
- Any decrease
- >0-<10 decrease
- 10-19 decrease
- \geq 20 decrease
- \geq 10 decrease and \geq LLN
- \geq 10 decrease and < LLN
- \geq 20 decrease and \geq LLN
- \geq 20 decrease and < LLN

LVEF results will also be listed with subject level details including absolute change from baseline.

Ocular Exams

For best corrected visual acuity (BCVA), summary statistics for the logMAR score at baseline and end of study treatment will be displayed separately by eye using mean, median, standard deviation, minimum and maximum. Changes of logMAR score from baseline to end of treatment visit, and maximum (worst) change from baseline will be summarized based on the following categories: no change/improved vision: a change from baseline <0.12 ; a possible worsened vision: a change from baseline ≥ 0.12 to <0.3 ; a definite worsened vision: a change from baseline ≥ 0.3 . Subjects with character values of visual acuity exam results will not be included in this summary.

Number and percentage of subjects who experienced corneal clinical signs will be summarized. Among subjects who experienced corneal clinical signs, number and percentage of subjects with/without reported corneal events will be provided. Visual acuity/ abnormal corneal exam results (eye level) at each visit, and incidence of corneal clinical signs and reported corneal events (subject level) during the study will be listed. The findings considered 'corneal clinical signs' were identified from the pre-defined list of choices in the eCRF.

Listing of abnormal conjunctival exam results, listing of abnormal slit lamp Lens and slit lamp anterior chamber exam results and listing of indirect fundoscopic exam and intra-ocular pressure results will be provided separately.

Constitutional Symptoms (or B-Symptoms)

A summary of the number and percentage of subjects with any constitutional symptom /B-symptom will be displayed by scheduled visits. A summary of improvement, i.e. number of subjects who had no symptoms at each post-baseline scheduled visit and had at least one at baseline, will also be provided.

A supporting listing will be provided.

Organ Examination

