16.6.3. Efficacy

Laboratory Parameters
Serum M-protein, Urine M-protein, Serum FLC

 • If a laboratory value which is expected to have a numeric value for summary purposes, has a non-detectable level reported in the database, where the numeric value is missing, but typically a character value starting with '<x' or '>x' (or indicated as less than x or greater than x in the comment field) is present, the number of significant digits in the observed values will be used to determine how much to add or subtract in order to impute the corresponding numeric value. 
 ○ Example 1: 2 Significant Digits = '< x' becomes x - 0.01 ○ Example 2: 1 Significant Digit = '> x' becomes x + 0.1 ○ Example 3: 0 Significant Digits = '< x' becomes x - 1

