16.7.2. Handling of Missing Data

Element	Reporting Detail
General	
 • Missing data occurs when any requested data is not provided, leading to blank fields on the collection instrument: 
 ○ These data will be indicated by the use of a blank in subject listing displays. Unless all data for a specific visit are missing in which case the data is excluded from the table. ○ Answers such as “Not applicable” and “Not evaluable” are not considered to be missing data and should be displayed as such.
Outliers	
 • Any participants excluded from the summaries and/or statistical analyses will be documented along with the reason for exclusion in the clinical study report.
Responder Analysis	
 • For endpoints which determine the percentage of responders, subjects with unknown/not evaluable or missing best overall response will be assumed to be non-responders, and will be included in the denominator when calculating the percentages.
Time to Event	
 • Because study treatment is dependent on the study endpoints (e.g., progression, i.e. not a fixed treatment duration), the length of treatment for each subject will depend on the efficacy and toxicity of the treatment, so the duration of treatment will vary across subjects. Similarly the duration of follow up will also vary. All available time-to-event data will be analyzed using suitable statistical methods; subjects with shorter treatment and follow-up due to the natural history of their disease or medical necessities of the treatment of their disease will not be considered to have missing time-to-event data.

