3.0482	All Treated	OLVEF1 A	Summary of Left Ventricular Ejection Fraction Change from Baseline (All Treated MM)	Report for: All Treated MM, (Summarize: Total).	SAC [A]
3.0483	All Treated	OLVEF1 A	Summary of Left Ventricular Ejection Fraction Change from Baseline (Part 2 NHL)	Report for: Part 2 NHL, (Summarize: only for 3.4 NHL)	SAC

CONFIDENTIAL

BMA117159

Safety: Tables					
No.	Population	IDSL / Example Shell	Title	Programming Notes	Deliverable [Priority]
Ocular Exams					
3.0490	All Treated	SAFE_T 1	Summary of Subjects Experiencing Corneal Clinical Signs (Part 1)	Report for: Part 1, (Summarize: by ascending dose level, Total).	SAC [A]
3.0491	All Treated	SAFE_T 1	Summary of Subjects Experiencing Corneal Clinical Signs (Part 2 MM)	Report for: Part 2 MM, (Summarize: only for 3.4 MM)	SAC [A]
3.0492	All Treated	SAFE_T 1	Summary of Subjects Experiencing Corneal Clinical Signs (All Treated MM)	Report for: All Treated MM, (Summarize: Total).	SAC [A]
3.0493	All Treated	SAFE_T 1	Summary of Subjects Experiencing Corneal Clinical Signs (Part 2 NHL)	Report for: Part 2 NHL, (Summarize: only for 3.4 NHL)	SAC
3.0500	All Treated	SAFE_T 2	Summary of Best Corrected Visual Acuity Test (BCVA) Scores (logMAR score) (Part 1)	Report for: Part 1, (Summarize: by ascending dose level, Total).	SAC [A]
3.0501	All Treated	SAFE_T 2	Summary of Best Corrected Visual Acuity Test (BCVA) Scores (logMAR score) (Part 2 MM)	Report for: Part 2 MM, (Summarize: only for 3.4 MM)	SAC [A]
3.0502	All Treated	SAFE_T 2	Summary of Best Corrected Visual Acuity Test (BCVA) Scores (logMAR score) (All Treated MM)	Report for: All Treated MM, (Summarize: Total).	SAC [A]
3.0503	All Treated	SAFE_T 2	Summary of Best Corrected Visual Acuity Test (BCVA) Scores (logMAR score) (Part 2 NHL)	Report for: Part 2 NHL, (Summarize: only for 3.4 NHL)	SAC
Death					
3.0570	All Treated	DTH1a	Summary of Deaths (Part 1)	Report for: Part 1, (Summarize: by ascending dose level, Total).	SAC [A]
3.0571	All Treated	DTH1a	Summary of Deaths (Part 2 MM)	Report for: Part 2 MM, (Summarize: only for 3.4 MM)	SAC [A]
3.0572	All Treated	DTH1a	Summary of Deaths (All Treated MM)	Report for: All Treated MM, (Summarize: Total).	SAC [A]

CONFIDENTIAL

BMA117159

Safety: Tables					
No.	Population	IDSL / Example Shell	Title	Programming Notes	Deliverable [Priority]
3.0573	All Treated	DTH1a	Summary of Deaths (Part 2 NHL)	Report for: Part 2 NHL, (Summarize: only for 3.4 NHL)	SAC
Constitutional B- Symptoms					

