	Definite worsened vision	xx (xx%)	xx (xx%)	xx (xx%)

Note: High scores are associated with worse vision, and low scores with better vision. No change/improved vision is defined as a change from baseline <0.12; a possible worsened vision is defined as a change from baseline >=0.12 to <0.3; a definite worsened vision is defined as a change from baseline >=0.3 logMAR score. For "End of study Treatment", summarize for subjects with ocular exam results at the end of study treatment; ocular assessment For "Change from baseline to end of study treatment", summarize for subjects with ocular exam results at baseline and the end of study treatment. For "Maximum (worst) change from baseline", summarize for subjects with ocular exam results at baseline and at least one post-baseline visit.

Subjects with "worse than 20/400" results will not be included in the summary.

PPD

Example: SAFE_T3
Protocol: BMA117159
Population: Part 1

Table x.xxxx
Summary of Symptom Impact and HRQoL Item Scores Part 1)

Item Score=Bone Pain Worst
Treatment: 0.03 mg/kg (N=200)

Planned Time		n	Mean	SD	Median	Min.	Max.
Baseline	Score	xx	xx.x	xx.xx	xx	xx	xx
Cycle 1 Day 1 to Day 8 Average	Score	xx	xx.x	xx.xx	xx	xx	xx
	Change from Baseline	xx	xx.x	xx.xx	xx	xx	xx
Cycle 1 Day 15	Score	xx	xx.x	xx.xx	xx	xx	xx
	Change from baseline	xx	xx.x	xx.xx	xx	xx	xx

Note: This mock up will be used for both summary of item scores and change from baseline. For summary of change from baseline, include baseline scores. Include Bone Pain Worst, Bone Pain Average, Fatigue worst in one summary table. This note dose not need to be included in the final output. Will add the notes to programming notes

PPD

Example: SAFE_T4
Protocol: BMA117159
Population: Part 1

Page 1 of 1
(Data as of: 30MAY2001)

Table X.XXXX
Summary of Human Anti-GSK2857916 Antibodies (ADA) Over Time

Visit	Category	Cohort 1 (x mg/kg)
	Results	(N=X)

CYCLE 1 WEEK 1

Screening ADA Result

n	X
POSITIVE	X (X%)
NEGATIVE	X (X%)

Confirming ADA Result

n	X
POSITIVE	X
NEGATIVE	X (X%)

Conclusive

n	X
NEGATIVE, CONCLUSIVE	X (X%)

Note: Negative, Conclusive is a Negative result in ADA assay (either negative screening or negative confirming assay result) and GSK2857916 total antibody concentration <25 ug/mL in pharmacokinetic sample collected at same time or same day prior to dosing as the ADA sample.

PPD

Example: SAFE_T5
Protocol: BMA117159
Population: Part 1

Page 1 of 1
(Data as of: 30MAY2001)

Table x.xxxx
Summary of Anti-GSK2857916 Antibodies (ADA)

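### The worst-change rows of the visual acuity table exclude results below 20/400, although from a baseline of 20/200 or better these are definite worsening by the plan's own cut-off

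*SAP*

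**What the plan says.** SAP section 8.7, under Ocular Exams, summarises BCVA as logMAR separately for each eye. It sorts change to end of treatment and maximum (worst) change into no change or improved, possible worsening and definite worsening. It then adds: "Subjects with character values of visual acuity exam results will not be included in this summary".

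The note to shell SAFE_T2 in Appendix 13 (section 16.13) names the case: "Subjects with 'worse than 20/400' results will not be included in the summary". The appendix prints this shell twice, and both printings carry the sentence. The same note says that higher scores mean worse vision and that "a definite worsened vision is defined as a change from baseline >=0.3 logMAR score". One of the two printings also has a block for change to last follow-up.

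Section 16.12.8 uses SAFE_T2 for Tables 3.0500 to 3.0503, the only summary tables of measured acuity. Acuity by eye and visit is also shown in listings 30.0260 and 30.0261. Section 16.7.2 adds a general rule for the study report: "Any participants excluded from the summaries and/or statistical analyses will be documented along with the reason for exclusion".

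**The concern.** The exclusion depends on the outcome and acts at the bad end of the scale. A row labelled as the worst change from baseline omits the worst results, although the category of many of them is certain.

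The rule is also written for subjects in a table laid out by eye. Read literally, one such result in one eye at one visit removes the subject from every row, including valid data from the fellow eye and from other visits.

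What is at stake is the rate of definite visual loss for a drug whose corneal events became an event of interest during the study (section 8.2). The primary objective is safety and tolerability, with the endpoint given in section 2.2 as "Adverse events (AE) and changes in clinical signs and laboratory parameters". That text does not name acuity, so the link to the primary endpoint is an inference. The tables of corneal events and corneal signs (3.0430 to 3.0433 and 3.0490 to 3.0493) count reported events and examination findings. They do not supply a rate of measured loss.

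**Working it through.** The SAP states no figure on this point, so there is none to reproduce.

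**Inputs.** The cut-off of 0.3 logMAR and the 20/400 limit come from the SAFE_T2 note. The starting acuities 20/25, 20/40 and 20/60 appear in the SAFE_L2 example listing. The planned maximum of 40 subjects in the Part 2 myeloma cohort is in section 3.1.2.1.1. All case counts below are assumptions.

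**Step 1: can the excluded result be classified?** logMAR = log10(Snellen denominator / 20), so 20/400 is log10(20) = 1.301. A result worse than 20/400 lies above that, and the loss exceeds 1.301 minus the baseline value.

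| Baseline | logMAR | Loss exceeds | Certain to reach 0.3? |
|---|---|---|---|
| 20/25 | 0.097 | 1.204 | yes |
| 20/40 | 0.301 | 1.000 | yes |
| 20/60 | 0.477 | 0.824 | yes |
| 20/200 | 1.000 | 0.301 | yes |
| 20/250 | 1.097 | 0.204 | no |

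Every baseline of 20/200 or better is therefore classifiable. From the three SAFE_L2 acuities, the guaranteed loss is about 2.7 to 4 times the cut-off.

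**Step 2: maximum-change row.** Suppose d of N eyes have definite worsening and x of those d are removed. The reported rate is (d − x)/(N − x), which is below d/N whenever x > 0 and d < N.

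| Assumed truth | x = 1 | x = 2 | x = 3 |
|---|---|---|---|
| 8/40 = 20.0% | 7/39 = 17.9% | 6/38 = 15.8% | 5/37 = 13.5% |
| 4/40 = 10.0% | 3/39 = 7.7% | 2/38 = 5.3% | 1/37 = 2.7% |

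Table 3.0500 is by dose level. After the single-subject run-in, section 3.1.1.1 says "the cohort will be expanded to 3 or more subjects at the same dose level". In a cohort of three, one removed case turns 1/3 (33.3%) into 0/2 (0%).

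**Step 3: fellow eyes.** The subject-level rule also removes fellow eyes, which may or may not have worsened. If y fellow eyes without definite worsening leave the same row, the rate becomes (d − x)/(N − x − y). From 8/40, x = 1 and y = 1 gives 7/38 = 18.4%, but x = 1 and y = 5 gives 7/34 = 20.6%. Dropping the affected eyes pulls their row down; dropping fellow eyes can push a row either way.

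**Step 4: time-point rows.** An eye still below 20/400 at end of treatment is a true case there, and removing it lowers the rate (8/40 to 7/39 = 17.9%). An eye that was below 20/400 mid-study and has since recovered is also removed under the literal rule, although it is no longer a case. That raises the rate (8/40 to 8/39 = 20.5%). The direction is therefore not fixed in these rows.

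**The case against.** An open-ended acuity result cannot enter a mean or a maximum, so some exclusion is proper. This stands for the continuous statistics, but the category rows need no numeric score.

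The cases are not hidden. The listings show them, section 16.7.2 requires exclusions to be documented with reasons, and each change block prints its own n, so a shortfall can be seen (mixed with missing data). Reported corneal events are also counted by maximum grade and action taken. All of this stands and lessens the consequence, but none of it gives a correct worst-change rate.

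Results below 20/400 may be rare or absent. The SAP gives no frequency, so that cannot be excluded. A percentage from a cohort of three would carry little weight in any case.

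Section 16.6.3 takes a different line for M-protein and light-chain values beyond a limit, using significant digits "to determine how much to add or subtract in order to impute the corresponding numeric value". That rule concerns efficacy laboratory values near an assay limit. It shows a bounded result can be kept, but it does not contradict the acuity rule.

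Two stronger readings are tempting. One is that the exclusion always lowers the definite-worsening rate; steps 3 and 4 show that this fails once fellow eyes or recovered eyes are removed. The other is that an eye going from 20/25 to 20/30 and then below 20/400 would be filed as unchanged or improved, because its remaining numeric change is only 0.079. That needs the single result to be dropped while the subject stays in. Both texts speak of subjects, so the wording does not support it.

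**Conclusion.** The point holds for the maximum-change row. Excluding an eye that falls from 20/200 or better to below 20/400 removes a certain case of definite worsening and understates that eye's rate, unless every evaluable eye worsened. For change to end of treatment and to last follow-up, the bias can go either way, and the subject-level wording discards usable data from the fellow eye and other visits.

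The size is unknown. The illustrations run from about 2 percentage points (one case dropped, assumed truth 20.0% or 10.0%) to about 7 (three dropped from 10.0%), and they rest on assumed counts in 40 subjects. The classification itself rests only on the Snellen-to-logMAR conversion and the plan's cut-off. The plan should be changed, but the cases stay traceable.

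**What to change.** Replace the exclusion sentence in section 8.7 and in both printings of the SAFE_T2 note with these rules:

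1. In the category rows, count a post-baseline result worse than 20/400 as definite worsening when that eye's baseline is 20/200 or better. In the maximum-change row this applies to a result at any post-baseline visit. In a time-point row it applies only when the result is at that time point.
2. Show as separate counts the eyes with such a result whose baseline is worse than 20/200 or non-numeric, and any other character values that cannot be classified.
3. Apply the exclusion per result, and only to the mean, SD, median, minimum and maximum, with the number left out shown for each eye and time point.
4. Keep the fellow eye and the subject's other numeric visits.

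The cost is one derivation rule, a revised note and a few table rows, all from data already collected. The downside is a slightly longer table and possibly a less favourable worsening rate.
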